## **11. QUALITY CONTROL**

### **11.1. INFORMATION FOR DATA COLLECTION**

All information required by the protocol shall be recorded on the observation books and an explanation shall be provided for each missing data. Data should be collected as they are obtained and transcribed into these books in a neat and legible manner.

Incorrect data found on the observation books will be clearly crossed out and the new data will be copied, next to the crossed-out information, accompanied by initials, the date and possibly justification by the person who is directing and monitoring the research or the authorized person who made the correction.

Data are collected on a paper CRF.

The data to be collected directly in the CRF will be:

- age, sex
- migraine diagnosis according to International Headache Society criteria
- number of days with headache per month
- duration and intensity of crises
- headache treatment medication per month
- HAD and HIT

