### 7.1. PRIMARY ENDPOINT

**Reduction of migraine crisis frequency of at least 50% after 3 months of treatment.**

The studied variable will be the monthly frequency of migraine crisis. Data collection will be done using a migraine agenda (annex 1), starting the month before inclusion and music therapy initiation. This agenda

should then be completed usually during study period under music therapy. During each monthly visit, a control will be done by the intern of general medicine associated to the study.

The primary endpoint will be obtained using the difference between mean crisis frequency during the month before music therapy initiation and the one obtained during the 3rd month of treatment.

A reduction of at least 50% at month 3 will be considered as music therapy efficacy on episodic migraine prevention.

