#### MIGRAINE DIARY

Please fill in the migraine calendar daily and specify each day:

Migraine

Headache intensity: mild, moderate or severe

Duration in hours of headache

Migraine treatments used

Date	Migraine/tension headache	Intensity	Duration	Treatments
D1				
D2				
D3				
D4				
D5				
D6				
D7				
D8				
D9				
D10				
D11				
D12				
D13				
D14				
D15				
D16				
D17				
D18				
D19				
D20				
D21				
D22				
D23				
D24				
D25				
D26				
D27				
D28				
D29				
D30				
D31				

## 16.2. APPENDIX 2

Please fill the 2 questionnaires below:

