3.1. PRIMARY ENDPOINT

Reduction of migraine crisis frequency of at least 50% after 3 months of treatment.

The studied variable is the monthly frequency of migraine crisis. Data collection is done using a migraine agenda (annex 1 of protocol), starting the month before inclusion and music therapy initiation. This agenda should then be completed usually during study period under music therapy. During each monthly visit, a control will be done by the intern of general medicine associated to the study.

The primary endpoint is obtained using the difference between mean crisis frequency during the month before music therapy initiation and the one obtained during the 3rd month of treatment. A reduction of at least 50% at month 3 is considered as music therapy efficacy on episodic migraine prevention.

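### The only frequency count listed for the CRF is headache days, which matches neither protocol definition of the primary endpoint and can include tension headache

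*Protocol*

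**What the plan says.** The primary variable is specific to migraine wherever it is defined. Protocol 7.1 states: "The studied variable will be the monthly frequency of migraine crisis". SAP 3.1 agrees: "The studied variable is the monthly frequency of migraine crisis". The Month 3 evaluation in Protocol 4.1 also names a migraine variable as the primary endpoint, but counts days with migraine instead of crises. Protocol 7.1 and SAP 3.1 name the patient's diary as the source, and Protocol 10.2 lists the diary among the source documents.

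Protocol 11.1 lists what goes directly into the CRF. Three items matter here: "number of days with headache per month", "duration and intensity of crises" and "headache treatment medication per month". The section opens with a general rule: "All information required by the protocol shall be recorded on the observation books".

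The diary in Appendix 1 has one row per day and a column headed "Migraine/tension headache". Its instructions use both terms: they ask about migraine and migraine treatments, but also for headache intensity and "Duration in hours of headache".

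Under Protocol 11.4 the data are entered, frozen by the principal investigator and sent to the methodological unit. Neither document says how diary rows become the CRF frequency value, whether rows marked as tension headache are excluded, or how daily rows are joined into crises.

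**The concern.** The trial plans to test one variable, and the list of CRF data names another. Settling whether the endpoint is crises or days would not cure this, because a headache day is still not a migraine day and the diary itself anticipates tension headache. The monitoring in Protocol 11.3 checks the CRF against source documents. A correctly added total of all headache days would pass that check.

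The 50% reduction is at stake, because Protocol 7.1 makes it the criterion of efficacy. An unchanged background of tension headache raises both months by the same amount and so shrinks the percentage fall. If tension headache itself changed, that change would be read as a change in migraine. The medication item is worded for headache treatment generally, so the same question arises there, though less strongly because the diary asks for migraine treatments.

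**Working it through.** **1. The units side by side.**
- Protocol 7.1, 9.1 and 9.2, and SAP 3.1, 5.1 and 5.2: migraine crises per month.
- Protocol 4.1, Month 3 evaluation: days with migraine.
- Protocol 11.1, CRF list: days with headache, type not specified.

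The third unit matches neither of the others. The list mentions crises only for their duration and intensity, not their number.

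**2. The plan's own figure.** Protocol 9.1 and SAP 5.1 give a baseline mean of 8 crises (SD 4), a 50% reduction, 90% power, alpha 5% and 20 patients. The difference is 8 × 0.5 = 4. The SD of the paired difference is not given. With correlation r between months it is 4 × √(2(1 − r)), which is 5.66 at r = 0. The two-sided normal formula then gives n = (1.960 + 1.282)² × (5.66/4)² = 21.01, so 22 patients, and power at n = 20 is 88.5%. The stated 20 is therefore reproduced approximately, for migraine crises, with r and sidedness assumed.

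**3. Effect on the 50% criterion.** Let T be the number of tension headache days per month. Assume that T is unchanged by treatment, that no tension headache falls on a migraine day, and that one crisis occupies one day. The documents give no value for T; 0 to 4 is an assumed range. If migraine falls from 8 to 4:

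apparent fall = 1 − (4 + T)/(8 + T) = 4/(8 + T)

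- T = 0: 4/8 = 50%
- T = 1: 4/9 = 44.4%
- T = 2: 4/10 = 40%
- T = 3: 4/11 = 36.4%
- T = 4: 4/12 = 33.3%

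Conversely, for headache days to fall by 50%, migraine must fall by (8 + T)/16. That is 62.5% at T = 2 and 75% at T = 4.

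**4. Effect on the Wilcoxon test.** If T is constant within a patient, the paired difference is (8 + T) − (4 + T) = 4. Every patient's difference is unchanged, and so is the signed-rank result. Power is lost only if tension headache days vary between months. Suppose they are independent Poisson counts with mean T in each month. The SD of the difference becomes √(32(1 − r) + 2T). Two-sided paired t power at n = 20, used as a stand-in for the Wilcoxon test, is then:

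| r | T = 0 | T = 2 | T = 4 |
|---|---|---|---|
| 0 | 85.1% (SD 5.66) | 80.7% (SD 6.00) | 76.5% (SD 6.32) |
| 0.5 | 98.9% (SD 4.00) | 96.6% (SD 4.47) | 93.3% (SD 4.90) |

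The correlation and the Poisson model are assumptions.

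**The case against.** The strongest reply is that the list in 11.1 is a summary and not a field specification. It omits other data that the protocol collects, such as the number of music sessions, and the general rule at the head of the section could cover a migraine count. The CRF form is not part of either document, and 11.4 does not say that the methodological unit receives only the listed items. The diary is the named source of the primary endpoint and lets the type of headache be marked. Headache may also be loose wording for migraine, since the migraine diary itself uses the word that way.

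Much of this stands, and it rules out several stronger readings:
- A reader might infer that tension headache days do enter the data and dilute the result. No passage says so; the text only leaves it open.
- A reader might infer that the CRF has nothing on crises. It lists their duration and intensity; only the count is missing. For the same reason, the list does not support extending the concern to those two secondary endpoints.
- A reader might infer that the Wilcoxon comparison is biased. With an unchanged background it is not.

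The reply does not remove the mismatch. A general duty to record everything creates no field, unit or counting rule, and the one frequency item that is named is the wrong variable. Elsewhere the protocol does write days with migraine, so a person completing the CRF could reasonably read headache as the wider term.

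**Conclusion.** The concern holds as a mismatch between the listed CRF item and the primary endpoint. As listed, the CRF contains no count of the primary variable under either definition, and its headache-day item can include non-migraine days.

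The consequence falls mainly on the 50% criterion. With 1 to 4 unchanged tension headache days per month, a true halving from 8 to 4 would appear as a fall of 44.4% to 33.3%; with none, there is no effect. These figures illustrate the size of a risk. They rest on an assumed tension headache rate, separate days and one crisis per day. The primary test would lose some power if tension headache varied between months. It would be shifted only if tension headache changed systematically, and the documents give no information on that. The mismatch should be corrected, but it does not invalidate the design or the sample size.

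**What to change.** 1. Reconcile Protocol 4.1 with Protocol 7.1 and SAP 3.1, so that the primary endpoint has one unit.
2. In Protocol 11.1, replace the headache-day item with the migraine count in that unit, for the reference month and Month 3, taken only from diary rows marked migraine. Record tension headache days in a separate field. The stated endpoints compare only these two months, so Month 1 and Month 2 fields are not required for them.
3. In the SAP, state that the medication count uses migraine-marked rows. If crises are the unit, also state how consecutive diary days are counted, because the diary has one row per day.

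The cost is a revised CRF page, a short SAP addition and slightly more transcription per patient. The diary already has a column for headache type, so no new visit or measurement is needed, and the planned 20 patients are unaffected.

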### **11.2. RESEARCH MONITORING**

The research will be monitored by a clinical research technician. He or she will be responsible for:

- research logistics and monitoring,
- reporting on its progress,
- checking the update of the CRF (request for additional information, corrections, etc.),

He will work in accordance with standard operating procedures, in collaboration with the Clinical Research Associate delegated by the administrator.

### **11.3. QUALITY CONTROL**

A clinical researcher appointed by the administrator regularly visits each center, when the research is set up, once or more in the course of the research according to the pace of inclusions and at the end of the research. During these visits, the following elements will be reviewed:

- compliance with the research protocol, the procedures defined therein and the legal instruments in force,
- quality of the data collected in the CRF: accuracy, missing data, consistency of the data with the source documents (medical records, appointment books, original laboratory results, etc.).

All visits will be subject to a written monitoring report.

### **11.4. DATA MANAGEMENT**

The data will be entered in Excel (or epidata for example). They will be managed by the investigator and stored on the computer server of the CHU de la Réunion, which will safeguard them. The data will be coded and frozen by the Principal Investigator before being forwarded to the Statistical Processing Methodological Support Unit.

### **11.5. AUDIT AND INSPECTION**

An audit may be carried out at any time by persons appointed by the manager and independent of the research managers. Its objective is to ensure the quality of the research, the validity of its results and compliance with the law and regulations in force.

The persons who direct and supervise the research agree to comply with the requirements of the administrator and the competent authority for an audit or inspection of the research.

The audit may apply to all stages of research, from the development of the protocol to the publication of results and the classification of data used or produced in the research.

## **12. ETHICAL AND REGULATORY CONSIDÉRATIONS**

### **12.1. COMPLIANCE WITH REFERENCE TEXTS**

Since the techniques and methods used in this research are usually carried out, it can be used as part of research to evaluate routine care as defined by Law No. 2004-806 of 9 August 2004 (Article L1121-1, paragraph 2 and Article R1121-3 of the Public Health Code).

The administrator and the person(s) who directs and supervises the research undertake that this research will be carried out in accordance with Law No. 2004-806 of 9 August 2004, as well as in accordance with Good Clinical Practice (I.C.H. version 4 of 1 May 1996) and the Helsinki Declaration (which can be found in its full version on the website <http://www.wma.net/en/30publications/10policies/b3/>).

The research shall be conducted in accordance with this Protocol. Except in emergency situations requiring specific therapeutic procedures, the person(s) who directs and monitors the research undertakes to comply with the protocol in every respect.

This research received the favorable opinion of the Committee for the Protection of Persons (CPP) of Bordeaux. This research is covered by the civil liability insurance of the CHU of The Reunion.

The data recorded during this research are computerized at the CHU de la Réunion in compliance with the law no. 78-17 of 6 January 1978 on information technology, files and freedoms as amended by Law 2004-801 of 6 August 2004. The CHU of The Reunion will send a request for an opinion to the Advisory Committee on the Processing of Information in the Field of Health Research (CCTIRS) and a request for authorization to the National Commission of Informatics and Liberties (CNIL).

### **12.2. PROTOCOL AMENDMENT**

Any substantial change, that is to say any change likely to have a significant impact on the protection of persons, on the conditions of validity and on the results of the research, on the interpretation of scientific documents that support the conduct of the research or on the manner in which it is conducted-This is the subject of a written amendment that is submitted to the Manager and the Data Management and Methodology Centre, if applicable, and the latter must obtain, prior to its implementation, a favorable opinion from the CPP.

Substantive changes, that is, those that have no significant impact on any aspect of the research, are provided to the CPP for information purposes.

All amendments are validated by the administrator, and by all research stakeholders involved in the amendment, prior to submission to the CPP. This validation may require the Scientific Committee meeting.

All amendments to the protocol must be brought to the attention of all health professionals who are involved in the research and who are committed to respecting its content.

---

### **13. RESEARCH DOCUMENTS AND DATA CONSERVATION**

The following documents related to this research are archived in accordance with Good Clinical Practice:

– By the people who realize the research:

**- for a duration of 15 years following the completion of the research** (research on drugs, medical devices or in vitro diagnostic medical devices or research not related to a product referred to in section L.5311-1 of the Public Health Code)

- Protocol and potential amendments
- CRF (copies)
- Source data of the patients
- All other documents or papers related to the research.

**- where applicable, for a period of 30 years following the completion of the research**

- Original copy of signed informed consent from participants

All these documents are the responsibility of the person conducting the search during the statutory archiving period.

– By the project manager:

**- for a duration of 15 years following the completion of the research** (research on drugs, medical devices or in vitro diagnostic medical devices or research not related to a product referred to in section L.5311-1 of the Public Health Code),

- Protocol and potential amendments
- CRF (original)
- All other documents or papers related to the research.

**- where applicable, for a period of 30 years following the completion of the research**

- A copy of the signed informed consent of the participants
- Documents related to serious adverse events

All these documents are under the responsibility of the project manager for the statutory archiving period.

No movement or destruction shall be carried out without the approval of the manager. At the end of the statutory archiving period, the manager will be consulted for destruction. All data, documents and reports will be subject to audit or inspection.

### **14. PUBLICATION RULES**

#### **14.1. SCIENTIFIC COMMUNICATIONS**

Analysis of the data provided by the centers is carried out by the Methodological Support Unit. This analysis results in a written report that is submitted to the project manager. This report allows the preparation of one or more publications.

Any written or oral communication of the results of the research must receive the prior consent of the person who directs and monitors the research.

The publication of the main results mentions the name of the project manager, of all health professionals who have included or monitored patients in the research. International rules for writing and publishing will be considered (Vancouver Convention, February 2006).

---

## 14.2. PATIENTS RESULTS COMMUNICATION

In accordance with Law No. 2002-303 of 4 March 2002, patients are informed, at their request, of the overall results of the research.

## 14.3. DATA CESSION

Data collection and management are carried out by the University Hospital Centre. The conditions for the transfer of all or part of the research database shall be decided by the research manager and shall be the subject of a written contract.

## 16. APPENDICES

### 16.1. APPENDIX 1

#### MIGRAINE DIARY

Please fill in the migraine calendar daily and specify each day:

Migraine

Headache intensity: mild, moderate or severe

Duration in hours of headache

Migraine treatments used

Date	Migraine/tension headache	Intensity	Duration	Treatments
D1				
D2				
D3				
D4				
D5				
D6				
D7				
D8				
D9				
D10				
D11				
D12				
D13				
D14				
D15				
D16				
D17				
D18				
D19				
D20				
D21				
D22				
D23				
D24				
D25				
D26				
D27				
D28				
D29				
D30				
D31				

## 16.2. APPENDIX 2

Please fill the 2 questionnaires below:

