#### - **Final evaluation at Month 3**

Diary data of the third month will serve for this evaluation according to the guidelines of the International Headache Society:

- number of days with migraine (primary endpoint)
- duration and intensity of migraine
- medication consumption
- emotional impact: score HAD
- functional impact: score HIT.

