## 7.7. FOLLOW-UP VISITS

Follow-up visits will be monthly done by the investigator, at Month 1, Month 2 and Month 3 after inclusion. During these visits, checks will be done regarding agenda migraine completion, patient motivation will be evaluated, and the number of music sessions done will be collected.

Impressions and feeling of the patient regarding music sessions will be collected.

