4. STUDY POPULATION

Intent-to-treat (ITT) Population: all the patients with at least on music session and sufficient completion of migraine diary to have evaluation at Month 3 of the primary endpoint.

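### The migraine diary does not separate a headache-free day from an uncompleted one, and no rule covers blanks, so more missed entries in Month 3 than in the reference month would bias the primary comparison towards benefit

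*Protocol*

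**What the plan says.** Protocol 7.1 defines the outcome and its source: "The studied variable will be the monthly frequency of migraine crisis" and "Data collection will be done using a migraine agenda (annex 1), starting the month before inclusion and music therapy initiation". Protocol 4.1 adds that "Diary data of the third month will serve for this evaluation according to the guidelines of the International Headache Society". The primary result is the reference-month frequency compared with the third-month frequency (Protocol 7.1 and 9.2; SAP 3.1 and 5.2).

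The form itself (Protocol, Appendix 1) carries the instruction "Please fill in the migraine calendar daily and specify each day". It then lists migraine, intensity, duration in hours and treatments. Rows run from D1 to D31. After the date, the columns are "Migraine/tension headache", intensity, duration and treatments. No entry is defined for a day without headache.

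Three provisions bear on completeness:

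- **Visits.** Protocol 7.4 schedules a diary check at Day 0 and Months 1, 2 and 3, and 7.7 repeats that at follow-up "checks will be done regarding agenda migraine completion".
- **CRF.** Protocol 11.1 requires that "an explanation shall be provided for each missing data". Its list of CRF items has the monthly number of headache days but no number of completed diary days.
- **Analysis set.** SAP 4 requires "sufficient completion of migraine diary to have evaluation at Month 3 of the primary endpoint", without a number of days and with no matching condition for the reference month.

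Neither document states whether a blank row is a zero, a missing value or something to be scaled or imputed.

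**The concern.** An empty row has two meanings that the form cannot tell apart. For an event count this matters, because an unrecorded event and an absent event contribute the same amount: nothing. With no count of completed days on the CRF, the analyst has no denominator with which to correct the total.

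The error has a direction only if non-entry differs between the two months being compared. The third month comes after two further months of daily recording, so lower completion then is plausible, although the documents give no figure. If that happens, the count falls without any clinical change. The design has one group, so nothing else in the study would show it. If the reference month were the less complete one, the bias would run the other way and hide a benefit.

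The ambiguity also weakens the plan's own safeguards. A completion check and a threshold for sufficient completion both need a definition of a completed day, and neither document gives one.

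**Working it through.** **Plan's own figure.** Protocol 9.1 and SAP 5.1 give mean 8, SD 4, a 50% reduction (difference 4), power 90%, alpha 5% and 20 patients. With independent months, n = 2 × SD² × (1.960 + 1.282)² / difference² = 2 × 16 × 10.51 / 16 = 21.01, so 22 two-sided; power at 20 is 88.5%. The stated 20 is close enough and is not disputed here.

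**Which provisions can resolve a blank row?** The form cannot, since no entry is defined for a headache-free day. The CRF cannot, since it has no field for completed days. The SAP cannot, since it has no rule. That leaves staff asking the patient at the visit, about days up to roughly a month earlier.

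**Size if blanks are left as zero.** Inputs from the documents: n = 20, mean about 8 per month, two months compared by the paired Wilcoxon test at 5% (taken as two-sided, because sidedness is not stated). Assumptions: 30-day months, no true change, blanks read as zero, and the non-entry rates themselves. A false reduction means p < 0.05 in the direction of a fall; the nominal rate is 2.5%.

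- Model A: patient rates normal with mean 8 and SD 2.7, limited to 4–14, the same rate in both months, binomial daily counts.
- Model B: beta-binomial counts matched to mean 8 and SD 4, with patient rates either constant or unrelated between months.

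| Non-entry, reference month vs Month 3 | A | B, constant rate | B, uncorrelated |
|---|---|---|---|
| 0% vs 0% | 2% | 3% | 3% |
| 0% vs 5% | 7% | – | – |
| 0% vs 10% | 17% | 17% | 9% |
| 0% vs 20% | 52% | 54% | 26% |
| 0% vs 30% | 87% | 86% | 50% |
| 10% vs 20% | 18% | – | – |
| 20% vs 30% | 20% | – | – |
| 10% vs 30% | 56% | – | – |
| 10% vs 10% | 3% | – | – |

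Hand check at 0% vs 20%: the spurious difference is 0.20 × 8 = 1.6. The simulated SD of the paired difference is 3.22 (B, constant). So 1.6 / (3.22/√20) = 2.22, and Φ(2.22 − 1.96) ≈ 0.60, slightly above the simulated 54%, as expected from a normal approximation at n = 20. With SD 5.19 (B, uncorrelated), 1.6 / (5.19/√20) = 1.38 and Φ(1.38 − 1.96) ≈ 0.28, against 26% simulated.

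**Against the 50% criterion.** With true reduction r and Month 3 non-entry f, the apparent reduction in the mean is 1 − (1 − r)(1 − f). Setting this to 0.5 gives f = 1 − 0.5/(1 − r): 50% for r = 0, 37.5% for r = 20%, 28.6% for r = 30%. Under model A with 10%, 20% or 30% non-entry and no true effect, the mean fell by half in 0%, 0% and 0.1% of trials. The share of individual patients with at least a 50% reduction rose from 9% with full entry to 14%, 21% and 30%.

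**The case against.** A reader might infer that the diary gives no means of marking a headache-free day, that forgotten days are counted as migraine-free, and that diary fatigue would therefore pass for efficacy. The documents do not support that reading, for these reasons:

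- The first diary column is open and daily entry is requested, so a patient could write none. What is missing is a defined entry. A legend on the printed form could also have been lost when the text was extracted from PDF, so the original layout should be checked.
- No text says blanks are zero. That is only what a plain count does when no rule is given.
- Completion is checked with the patient present at every visit from Day 0, and staff can ask about an empty row. The check has value, although it rests on recall.
- The reference month need not be freshly trained and complete. Protocol 7.5 places screening between 4 months and 1 month before inclusion, and the diary is the one the team usually uses. Both months may have gaps, and only the difference between them biases the result.
- Missed entries at the rates examined would almost never produce the 50% fall in the mean that Protocol 7.1 treats as efficacy.
- The calculation counts days, whereas Protocol 7.1 names crises. A crisis lasting several days survives one unentered day, so a crisis count would be less sensitive.

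All of this stands and limits the claim. It does not remove the ambiguity of a blank row, the absence of a completed-day count, or the exposure of the Wilcoxon test. That test is the only one specified for the primary endpoint, and it responds to any systematic fall.

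**Conclusion.** The point holds in a conditional form. Headache-free and uncompleted days are not distinguished, and neither blank handling nor sufficient completion is defined. If unentered migraine days are more frequent in Month 3 than in the reference month, the primary test is biased towards benefit. The gap between the two months drives the size: a gap of 10 percentage points gives a false significant reduction in about 17–20% of trials when patients' underlying rates are stable (about 9% with uncorrelated months and a complete reference month). The 52% and 87% figures require a complete reference month and 20% or 30% non-entry in Month 3. With equal non-entry the error is about 3%, close to nominal.

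These figures illustrate the mechanism and do not predict this trial, because actual non-entry is unknown. They assume that blanks stay as zero and that visit queries recover nothing. This is an inexpensive improvement that should be made before recording starts, because the two meanings of a blank cannot be reliably separated afterwards.

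**What to change.** 1. **Diary:** add a no-headache-today tick to every row, on the forms for the reference month and for the treatment months.
2. **Visits:** count a row as completed only if it has that tick or a headache entry, and query blank rows at Day 0 and Months 1, 2 and 3.
3. **CRF:** record the number of completed diary days for each month.
4. **SAP 4:** replace sufficient completion with a minimum number of completed days, applied to both the reference month and Month 3.
5. **SAP 5.2:** report the primary comparison twice, with blanks as zero and per 30 completed days, and tabulate completion by month.

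The cost is one tick box, one CRF field per month, a few sentences in the SAP and a few seconds a day for the patient. Some days will be classed as missing.

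Scaling to completed days is not neutral either, since it assumes that blanks are unrelated to headache. If a patient with 8 migraine days leaves 20% of the 22 free days unticked (4.4 days), the scaled figure is 8 / 25.6 × 30 = 9.4 instead of 8. Reporting both versions shows whether the conclusion depends on the blanks.

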## 7.2. SECONDARY ENDPOINTS

### - Reduction of crisis intensity and duration, as well as medication consumption.

Crisis intensity (mild, moderate, severe), duration in hour, and the number of treatments taken will be collected in the migraine agenda (annex 1) filled by the patient. These variables will be compared between the month before music therapy initiation and the 3rd month of treatment.

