3.2. SECONDARY ENDPOINTS

- Reduction of crisis intensity and duration, as well as medication consumption.

Crisis intensity (mild, moderate, severe), duration in hour, and the number of treatments taken are collected in the migraine agenda (annex 1 of protocol) filled by the patient. These variables will be compared between the month before music therapy initiation and the 3rd month of treatment.

- Reduction of functional and emotional impact.

Questionnaires HAD and HIT (annex 2 of protocol) will be completed with the investigator during the inclusion visit before initiation of music therapy, and at Month 3 visit.

- Questionnaire HAD to evaluate emotional impact (national reference HAS « chronic pain: recognize chronic pain syndrome, evaluate it and guide the patient »)
- Questionnaire HIT to evaluate functional impact (guideline of the International Headache society)

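### Crisis duration, a secondary endpoint, cannot be identified from a diary with one undefined duration cell per date and no mark linking one date to the next

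*Protocol*

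**What the plan says.** Protocol 7.2 names the variable and its source: "Crisis intensity (mild, moderate, severe), duration in hour, and the number of treatments taken will be collected in the migraine agenda". SAP 3.2 says the same: "Crisis intensity (mild, moderate, severe), duration in hour, and the number of treatments taken are collected in the migraine agenda". The contrast is before versus after: "These variables will be compared between the month before music therapy initiation and the 3rd month of treatment". SAP 5.2 tests it with the paired Wilcoxon signed rank test used for the primary endpoint. Protocol 11.1 lists "duration and intensity of crises" among the data for the CRF, so there too the unit is the crisis.

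The only source named for duration is the Appendix 1 diary. It has rows D1 to D31 and the instruction "Please fill in the migraine calendar daily and specify each day". The item itself reads "Duration in hours of headache". There is no start time, no stop time and no continuation mark.

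Protocol 7.4 lists training on the diary at screening but does not give its content. Protocol 7.7 has the monthly visits check that the diary is filled in. Neither document says how dated rows are turned into crises, or how a patient's crises are summarised over the month.

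**The concern.** The endpoint is per crisis and the record is per date, with nothing to join them. Take two consecutive rows showing 6 h and 12 h. They may be one 18 h crisis that began at 18:00, or two separate crises. The patient's mean crisis duration is then either 18 h or (6 + 12)/2 = 9 h, and the form cannot say which. If the patient took the cell to mean the whole attack, the same crisis might appear as a single 18.

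This is more than a missing line in the SAP. A derivation rule written later can choose between these readings, but it cannot recover which one was true, because the form never asks. At stake is the reported change in crisis duration, part of a named secondary objective (protocol 3.2, SAP 2.2).

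**Working it through.** **The plan's own figures.** The documents give no figure for crisis duration. Their one computed figure, 20 patients, concerns crisis frequency, and nothing below depends on it. The only planning input borrowed is 8 crises per month with a 50% reduction, so 8 to 4 (protocol 9.1, SAP 5.1). All durations and onset times below are assumptions.

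**Step 1. Rows hold that date's hours and each row is used as entered.** If onset is uniform over the day, a crisis of d hours occupies on average 1 + d/24 rows, so the mean entry is d/(1 + d/24).

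- 6 h: 6/1.25 = 4.8 h
- 12 h: 12/1.5 = 8 h
- 24 h: 24/2 = 12 h
- 48 h: 48/3 = 16 h

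A true halving from 24 to 12 h is recorded as 12 to 8 h, a fall of 33%. From 48 to 24 h it is 16 to 12 h, a fall of 25%. For short crises the distortion is small: 6 to 3 h is recorded as 4.8 to 2.67 h, a fall of 44%.

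**Step 2. Adjacent headache days are merged into one crisis.** Suppose each crisis stays within one date and k headache days fall at random in a 30-day month. The expected number of runs of consecutive days is k(31 − k)/30.

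- k = 8: 8 × 23/30 = 6.13 runs, so 8/6.13 = 1.30 days per apparent crisis
- k = 4: 4 × 27/30 = 3.6 runs, so 4/3.6 = 1.11 days per apparent crisis

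The ratio 1.11/1.30 is 0.85. Apparent duration falls 15% although no crisis became shorter.

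**Step 3. Simulation of competing rules.** Assumptions: gamma durations with coefficient of variation 0.5, limited to 1–72 h; crises placed at random in 30 days with at least 4 h between them; hours split at midnight; 3,000 patient-months per setting. About 25%, 49% and 80% of crises cross midnight at mean durations of 6, 12 and 24 h. Entries are mean hours; percentages come from unrounded means.

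| Crises per month | True duration | Each row a crisis | Starting-day hours only | Adjacent days merged |
|---|---|---|---|---|
| 8 → 8 | 24 → 12 h | 12.7 → 8.6 (−32%) | 11.0 → 8.2 (−25%) | 39.4 → 18.3 (−54%) |
| 8 → 8 | 12 → 6 h | 8.5 → 5.2 (−39%) | 8.3 → 5.0 (−39%) | 18.2 → 8.7 (−52%) |
| 8 → 4 | 24 → 12 h | 12.7 → 8.3 (−35%) | 11.0 → 8.3 (−25%) | 39.4 → 14.4 (−63%) |
| 8 → 4 | 12 → 6 h | 8.6 → 5.0 (−41%) | 8.3 → 5.0 (−39%) | 18.2 → 7.2 (−60%) |
| 8 → 4 | 24 h, unchanged | 12.7 → 12.2 (−4%) | 10.9 → 10.9 (0%) | 39.3 → 29.4 (−25%) |
| 8 → 4 | 12 h, unchanged | 8.6 → 8.3 (−3%) | 8.3 → 8.4 (0%) | 18.1 → 14.7 (−19%) |
| 8 → 4 | 6 h, unchanged | 5.2 → 5.1 (−3%) | 5.1 → 5.1 (0%) | 8.8 → 7.2 (−18%) |

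With 4 crises in both months and 24 → 12 h, the three rules give −32%, −24% and −51%.

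**Step 4. Whole attack written once.** If every patient does this, a true 50% fall is recorded as 50%.

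**Step 5. Total headache hours per month.** The midnight split does not affect this total, but it mixes duration with frequency. When both halve, it falls by 75%.

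**The case against.** The strongest reply is that the form never says the cell means hours on that date. A patient may enter the whole attack once, and then there is no bias. This stands, and it rules out a tempting inference: that every crisis passing midnight is scored too short, so that a real fall is understated. The documents support that only if rows hold that date's hours and are used as entered. Filling in the diary each day makes such a reading natural but does not compel it, and merging adjacent days pushes the error the other way. If patients differ in how they read the cell, the error cannot be detected.

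A second reply is that the analyst can add up adjacent days, or the investigator can ask at the monthly visit, since the CRF records crises. Adding up is possible but, as Step 2 shows, exchanges one bias for another. Asking is possible too, but no linking procedure is written. It would rest on the patient's memory of individual nights at visits a month apart.

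A third reply is that this is one of several secondary endpoints with no stated power, and that the test would survive. That largely stands for big effects. A simulation of 20 patients treating each row as a crisis gave paired Wilcoxon power of 98–100% for halved durations, against about 100% with true durations. For falls of 20–30% the loss was in the order of ten percentage points. These results rest on assumed variability, so a material loss of power should not be inferred. What suffers is the meaning and size of the reported fall.

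Finally, the documents give no durations, and for crises of a few hours the effect of using rows as entered is minor. That is fair.

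**Conclusion.** The point holds as a problem of identifiability, not of a known direction. Crisis duration cannot be derived unambiguously from this diary, and neither document supplies a rule. With assumed mean durations of 6–24 h and 8 crises in the reference month, a true 50% fall may be reported as anything from about 25% to about 63%, depending on a choice nobody has written down. Merging adjacent days can also report a fall of about 15–25% where only frequency dropped from 8 to 4. These sizes rest on assumed durations, random onset and random placement within the month; the mismatch between form and endpoint rests on the documents alone.

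It deserves correction because the missing information cannot be reliably recovered after the diary is filled in. It is not critical, because the endpoint is secondary. The undefined step from dates to crises also touches the primary variable, which protocol 7.1 counts in crises and protocol 4.1 in days with migraine, but that is a separate matter.

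**What to change.** In Appendix 1, define the duration cell as hours of headache on that date, and add one tick column: *headache continues from the previous day (yes/no)*. Use the same form in the reference month and in Months 1–3. In protocol 7.2 and SAP 3.2, define crisis duration as the sum of hours over linked consecutive rows, averaged over the patient's crises in the month.

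For diaries already completed without the tick, do not report the variable as crisis duration. Report it as hours of headache per headache day, with the caveat that the cell was not defined as that date's hours.

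The cost is one column on a paper form, one sentence in each document, one more daily tick for patients, and the summing of linked rows at data entry. No visits, patients or staff are added. One limit remains: two attacks on the same date still share a row and would be counted together.
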